- 6. Benefits: Utilizing AB plasma as the initial resuscitation fluid may increase the likelihood of survival, decrease multiple organ failure, and decrease the overall need for blood products, especially in the setting of activation of the massive transfusion protocol. Furthermore, implementation of this study may help patients in the future by giving important information about the treatment of acute blood loss and initial resuscitation in trauma. Benefits for patients in the control arm include intensive surveillance of the acute coagulopathy of trauma that may result in further appropriate medical treatment
- 7. Risk-Benefit analysis: Risks to the subject include reaction to risk of transmission of blood-borne pathogens, which is minimal, risk of reaction to blood transfusion, venipuncture, inadvertent release of PHI, or unforeseen happenings. Benefits include the potential to improve outcome in the critically injured with acute coagulopathy of trauma as well as decreased need for blood products. The risks of blood transfusion is small, but this specific trauma population that is severely injured and in hemorrhagic shock will likely receive transfusion of multiple blood products, including plasma, regardless of the type of initial resuscitation fluid. By transfusing AB plasma early as a resuscitation fluid, we may be able to slow down the ACoT, leading to a decreased number of transfused blood products. As stated above, transfusion of blood products in the first 12 hours is an independent risk factor of mortality.⁶³ Furthermore, using the same inclusion criteria as in the recent ROC hypertensive HTS trial,⁶⁷ mortality in this study is expected to exceed one in four. At the same time, massive pRBC infusion remains a major risk factor for MOF^{36, 38, 99} while plasma transfusion does not.
- 8. Adverse Events
 - a. The PRA team will be responsible for identifying and documenting adverse reactions. They will ask the principal investigator and the attending physician for the relatedness of the adverse reaction to study

and if they should be reported to the appropriate agencies. The DSMB as well as the RM will evaluate the relatedness of adverse reactions. All product related SAE's will be reported to the FDA within 15 calendar days.

b. The definitions of serious adverse events are from our MOF database and the Glue Grant study and in Table 4:

Table 4: Definitions of Serious Adverse Events			
Serious Adverse Events	Presentation and Treatment		
Bloodstream Infections	Bacteriologic confirmation of a recognized pathogen from one or more blood cultures and organism cultured is not related to an infection at another site. If a skin contaminant is cultured (diptheroids, Bacillus sp, Propionobacterium sp, coagulase- negative staphylococci), the organism must be cultured from at least two cultures within a 48 hour period and the patient has at least one of: fever>38.5°C, WBC>10,000 or <3,000/mm ³ , SBP<90 mmHg or >25% drop in SBP.		
Myocardial infarction	Acute, irreversible myocardial injury documented by both: 1) abnormal increase in CK-MB or troponin, and 2) new, serial T-wave, S-T segment or Q wave EKG abnormalities.		
Cerebral infarction	New neurologic deficit not present on admission which is sudden or rapid in onset and last >24 hours or until death and confirmed as an infarction by CT or MRI.		
Lung dysfunction	Denver lung dysfunction score $\geq 2^*$ (P/F ratio adjusted for altitude ≤ 165)		
Renal dysfunction	Denver renal dysfunction score $\geq 2^*$ (serum creatinine ≤ 2.5 mg/dL)		
Multiple Organ Failure (MOF)	Denver MOF score ≥3 for 1 day*		
Febrile non-hemolytic reaction	A temperature elevation of \geq 1°C or 2°F occurring during or shortly after a transfusion and in the absence of any other pyrexic stimulus. Symptoms treated with antipyretics		
Allergic reactions	Mild or self-limiting urticaria or wheezing that usually respond to antihistamines.		
Anaphylactoid/anaphylactic reactions	Hypotension, tachycardia, nausea, vomiting and/or diarrhea, abdominal pain, severe dyspnea, pulmonary and/or laryngeal edema, and bronchospasm and or laryngospasm. Immediately treated with epinephrine.		
Transfusion-related acute lung injury (TRALI)	Acute onset of hypoxemia within 6 hours of a blood component transfusion, bilateral infiltrates on chest x-ray, and the exclusion of preexisting acute lung disease or transfusion-associated circulatory overload (TACO) in a patient without clinical risk factors for the development of ALI.		
Bacterial sepsis	High fever ($\geq 2^{\circ}$ C or $\geq 3.5^{\circ}$ F increase in temperature), severe chills, hypotension, or circulatory collapse during or shortly after transfusion suggests possible bacterial contamination and/or endotoxin reaction. Treated with discontinuation of the transfusion and aggressive therapy with broad-spectrum antimicrobials and vasopressor agents, if necessary.		

*Denver postinjury MOF Score⁸⁰

TABLE 1.	Denver	postiniu	rv MOF	score

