PROTOCOL #: 12-1349 VERSION DATE: 12/27/2016

COMIRB Protocol

(Use Protocol Manager on the COMIRB Website)

COLORADO MULTIPLE INSTITUTIONAL REVIEW BOARD [name] [contact] [contact]

Project Title: Control Of Major Bleeding After Trauma (COMBAT): A prospective, randomized comparison of fresh frozen plasma versus standard crystalloid intravenous fluid as initial resuscitation fluid

Principal Investigator: [name].

This study is sponsored by the DOD's Telemedicine & Advanced Technology Research Center (TATRC).

I. Study Main Objective: The main objective of the study is to determine the efficacy of administering plasma (specifically AB-FP24) during field resuscitation compared to current treatment policy or standard of care (SOC) in which normal saline is infused in the pre-ED phase. This Phase 2 trial will provide preliminary evidence to potentially support Phase 3 trials with large study populations.

Study aims:

- 1) To determine if plasma-first resuscitation of severe hemorrhagic shock attenuates the acute coagulopathy of trauma.
- 2) To determine if plasma-first resuscitation of severe hemorrhagic shock improves metabolic recovery.
- 3) To determine if plasma-first resuscitation of severe hemorrhagic shock decreases overall blood product transfusion and reduces the incidence of acute lung injury, multiple organ failure, and mortality. In relation to the efficacy of plasma-first resuscitation, we will assess whether waveform information can help predict activation of the massive transfusion protocol.

II. Background and Significance:

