Factor XII (%)					82	94
AT III (%)			č.		96.3	
Protein C (%)	107±20	107±19	88±16	89±17	103.8	
Protein S (%)	97±18	90±22	92±18	78±19	73.7	

Recent proteomic analyses of injured patients have demonstrated that following injury these patients have decreased levels of circulating anti-proteases and increased levels of intracellular enzymes, which may directly affect coagulation and influence organ injury through the protease-activated receptors on endothelial cells, and common intracellular proteins, like actin, which, if polymerized, may cause acute lung injury (ALI).⁵⁷⁻⁵⁹ Interestingly, our recent proteomic analysis of FP24 demonstrates an abundance of numerous anti-proteases, α_2 -macroglobulin and α_1 -antitrypsin, which have the ability to oppose protease effects of coagulation and PARS as well as gelsolin, an extracellular protein that "solubilizes" actin filaments that could induce endothelial injury.^{57, 58, 60}

Overall, there is, however, a limited supply of AB type plasma. AB plasma is the universal plasma donor for patients that have not yet had blood typing and will be the only type of plasma used for this study regardless if it is FFP or FP24. According to the DHMC adult transfusion guidelines, thawed plasma is given in patients with massive transfusion or life threatening bleeding with clinical evidence of coagulopathy, regardless of PT/PTT levels and only AB plasma will be infused.

The Circular of Information for the Use of Human Blood and Blood Components, prepared by the AABB, American Red Cross, America's Blood Centers, and the Armed Services Blood Program and approved by the FDA, states the indications for infusion of FP24 are the same as FFP except for treatment of deficiencies of Factor VIII and Factor V.⁶¹ Under the section for Dosage and Administration, "FFP must be thawed in a water bath at 30 to 37 degrees Celsius or in an FDA-cleared device."

In the traditional method of thawing plasma, the blood bank often uses a water bath at 37 degrees Celsius and takes an average of 20 minutes for 2 units.⁶² After thawing, the thawed plasma must be kept at 4 degrees Celsius up to 24 hours. It has

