- 4. Description of population to be enrolled: Enrollment will include acutely injured trauma patients in severe, presumed hemorrhagic shock. Patients will be enrolled based on initial field vital signs. Inclusion criteria: Age>18 years, acutely injured, with presumed hemorrhagic shock from acute blood loss defined as SBP<70 mmHg or SBP 71-90 mmHg with HR>108 beats per minute. *Exclusion criteria:* Visibly or verbally reported pregnant women, age<18 years, known prisoners, unsalvageable injuries (defined as asystolic or CPR prior to randomization), isolated GSW to the head with a GSW < 5 (a highly lethal injury that is not primarily due to acute blood loss), known or religious objection to blood products, the patient has an opt-out bracelet or necklace, or a family member present at the scene objects to the patient's enrollment in research. Pregnant Women: It is not feasible to perform a pregnancy test after determination of eligibility because of life threatening injuries. In the community consultation, we will advise nonvisibly pregnant women opt out of the study. We will exclude any women of childbearing age that is visibly pregnant. Prisoners: Only known prisoners at the time of enrollment will be excluded. Patients who are under a police hold or become a prisoner during hospitalization will be included in the study. In the acute trauma setting, patients may be placed on a police hold at any time during hospitalization. The hold may be temporary for a short time or for an indeterminant length of time. Paramedics may not know who will be placed under a police hold. Thus, ethically, these patients cannot be coerced for enrollment,. Patients placed on a police hold during hospitalization have already been randomized to the standard or experimental group. The study team would collect serial blood samples and follow up with the patient at 28 days. Rationale for hemorrhagic shock entry criteria: The criteria were based on the last ROC trial⁶⁷, which in turn were chosen based on a previous trial⁶⁸ that showed that SBP≤90mmHG was not as "specific marker of hypovolemic shock", while the alternative criteria led to a larger proportion of patients requiring massive transfusion. Thus, although the traditional marker of severe shock, SBP<90, we plan to use the same entry criteria as the ROC trauma trial so the populations of the two studies may be compared, which will enhance generalizability of the findings.

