transfusion include febrile non-hemolytic transfusion reaction (1.1% to 2.5%), hemolytic transfusion reactions (1:1,250,000), transmission of blood borne pathogens (See Table 2), transfusion-related lung injury (TRALI) (8.1 per 100,000), transfusion associated circulatory overload (TACO) (2-3 per 100).¹¹² A blood transfusion may also result in a reaction that includes fever, chills, or hives. Although uncommon, the patient may experience this type of reaction as the result of receiving the incorrect type of blood. By using AB type of plasma, this risk is minimized. This risk is minimized in the blood bank by a questionnaire to exclude donors who are at risk of having a blood borne pathogen as regulated by the FDA under 21CFR 640 subpart G. The donated blood is also tested in the laboratory for infectious diseases.

A blood transfusion may increase the likelihood of developing an infection while the patient is in the hospital, may exaggerate how the patient's body responds to injury, and may increase the patient's risk of internal organ failure after his/her injury.

Excessive transfusions place patients at higher risk of hypervolemia, and pulmonary edema, but this risk also exists for patients who receive excessive intravenous fluids. The risk of 2 units of AB-FP24 as initial resuscitation leading to cardiac failure, hypervolemia and pulmonary edema is low as it is a smaller volume (500ml) than the standard 2 liters of crystalloid intravenous fluid. These risks exist with transfusions of any blood products

- Risk of Inadvertent Release of Protected Health Information (PHI): This risk is minimized by using a unique patient identifier and role based security for the database. All hard copies will be kept locked in the research office or be destroyed.
- **3.** Venipuncture risk: In most cases blood will be drawn from an intravenous line (I.V.) already placed as part of the patient's standard medical care. In the event the patient does not have an I.V., blood will be drawn using a method known as venipuncture. This procedure consists of placing a small needle in a vein in the patient's arm to withdraw blood. Risks associated with drawing blood from the patient's arm include pain, bruising, lightheadedness, and rarely infection.

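### Table 4's TRALI row fits few if any shock patients and TACO has no row, so transfusion-associated lung events cannot be reliably classified, though lung injury overall is still counted by arm

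*Combined protocol and SAP*

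**What the plan says.** Table 4 (Section IV.N.8.b) defines eleven serious adverse events. The TRALI row needs acute hypoxemia within 6 hours of a blood component and bilateral infiltrates on chest x-ray. It also needs "the exclusion of preexisting acute lung disease or transfusion-associated circulatory overload (TACO"), and it applies only "in a patient without clinical risk factors for the development of ALI". No row is given to TACO.

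The same table has a row for lung dysfunction, based on the "Denver lung dysfunction score" at 2 or more (altitude-adjusted P/F ratio of 165 or less). That row sets no condition on cause, timing or risk factors.

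Section IV.A.4 describes the population: "Enrollment will include acutely injured trauma patients in severe, presumed hemorrhagic shock". Section IV.N.1 gives background risks of 8.1 per 100,000 for TRALI and, in its words, "transfusion associated circulatory overload (TACO) (2-3 per 100"), without saying whether either is per unit or per patient. Section IV.N.8.a states: "All product related SAE's will be reported to the FDA" within 15 calendar days.

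**The concern.** The TRALI condition suits patients who have no other reason for lung injury. This trial enrols patients who have one, and the protocol says as much: the third study aim asks whether plasma "reduces the incidence of acute lung injury, multiple organ failure, and mortality". A row that turns on the absence of ALI risk factors will then be empty, or nearly so, whether or not plasma causes lung injury.

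The TACO gap compounds this. The TRALI row removes TACO cases, and nothing in Table 4 takes them in, although on the protocol's own figures TACO is much the more frequent of the two.

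The stake is how the safety record will be read. Section III.B presents donor selection for FP24 as a way of lowering the TRALI risk, so a TRALI count is likely to be quoted as evidence. The November 2016 addendum in Section IV.E already supports continuing the trial partly on the ground that adverse events have not increased. The trial also runs under exception from informed consent, which raises the value of a clear account of product harms.

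**Working it through.** The plan gives no figure to reproduce on this point. The check sets the definitions beside the population, follows an event through Table 4, and then gauges scale.

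**1. Condition against population.**

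| TRALI row requires | What the protocol says of its patients |
|---|---|
| No clinical risk factors for ALI | Acutely injured, in severe presumed hemorrhagic shock (IV.A.4) |
| | ALI is an outcome that plasma is hoped to reduce (Section I, aim 3) and is measured as ALI-free days (IV.G.3) |
| | Proteins released after injury are linked to ALI (III.B and IV.G.4) |
| | The acidosis endpoint (IV.F.4) cites a study whose title links initial metabolic acidosis to later ALI in severe trauma; mean base deficit at the second interim was 11.2 and 9.2 mEq/L in the two groups (IV.E addendum) |

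The documents do not list which clinical risk factors count, so the supportable conclusion is that few or none qualify.

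**2. Following an acute event with bilateral infiltrates within 6 hours of study plasma.**

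- ALI risk factor present, P/F ratio 165 or less: not TRALI; recorded as Lung dysfunction.
- ALI risk factor present, P/F ratio above 165: not TRALI and not Lung dysfunction. The Denver score table makes 165-208 grade 1, and the row starts at grade 2. No lung row applies.
- Circulatory overload: excluded from TRALI; recorded as Lung dysfunction only if the P/F ratio is 165 or less.

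The only other row that mentions pulmonary edema is the anaphylactic one, within an allergic picture treated with epinephrine. It does not serve for TACO.

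**3. Scale.** Inputs: 112 patients per group (IV.E addendum), two study units each, so 2 x 112 = 224 units; risks from IV.N.1. Because the denominator is not stated, both readings are shown as assumptions. Expected count = n x p; P(at least one) = 1 - (1 - p)^n.

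| Event | Reading | Expected | P(at least one) |
|---|---|---|---|
| TRALI, p = 0.000081 | per patient, n = 112 | 112 x 0.000081 = 0.009 | 0.9% |
| TRALI | per unit, n = 224 | 224 x 0.000081 = 0.018 | 1.8% |
| TACO, p = 0.02 to 0.03 | per patient, n = 112 | 2.24 to 3.36 | 90% to 97% |
| TACO | per unit, n = 224 | 4.48 to 6.72 | 99% to 99.9% |

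These cover the study units alone. The figures are for scale only, since Section IV.N.1 itself judges the overload risk from the 500 ml study volume to be low. On them, the missing TACO row affects more events than the TRALI condition.

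**4. What a zero TRALI count could show.** If all 112 plasma patients could qualify, zero events would put an approximate upper 95% limit of 3/112 = 2.7% on the rate. If only m of them lack ALI risk factors, the limit is about 3/m among those m, and nothing is learned about the other 112 - m. The protocol gives no m, and step 1 suggests that it is small.

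**The case against.** The strongest reply is that lung injury from plasma is already counted. The Lung dysfunction row applies to both arms whatever the cause. ALI-free and ventilator-free days are compared by arm (IV.G.3). Arterial blood gases are scheduled at ED arrival and at 2, 4 and 6 hours (IV.C.1). In a randomised trial an excess can show in these comparisons without labelling individual cases. This stands. A reader might infer from Table 4 that lung injury after study plasma cannot be counted at all; the documents do not support that.

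Four other inferences also go too far:

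- **That the DSMB could not see an excess.** Section IV.I.2 gives it outcomes and any potential adverse events by group.
- **That the FDA route is closed.** Under IV.N.8.a the investigator, the attending physician, the DSMB and the Research Monitor all consider relatedness, and none is bound by the Table 4 label. Section IV.K.3 also names respiratory distress and circulatory overload as signs of a transfusion reaction, and sends suspected reactions to the Blood Bank and pathology.
- **That no enrolled patient could qualify.** ALI risk factors are not listed, shock is presumed from field vital signs, and only 55% and 61% of the two groups needed transfusion (IV.E addendum).
- **That TRALI is a safety endpoint.** It is one of eleven defined events.

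It can also be said that zero TRALI would be the likely result under any definition, since only 0.009 to 0.018 cases are expected. That is right at background risk. The purpose of the row, however, is to reveal a rate well above background, and it is poorly able to do so.

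The alternatives leave a gap. The Lung dysfunction row has no time window or transfusion link and misses P/F ratios above 165. ALI-free days is a 28-day exploratory measure in which a 6-hour event is mixed with later lung failure and death. The reaction pathway in IV.K.3 names overload without criteria.

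**Conclusion.** The concern holds as a weakness in classification. As written, Table 4 would record few or no TRALI cases, and no TACO under its own name, whatever happens. Acute transfusion-associated lung events therefore cannot be reliably sorted, some with a P/F ratio above 165 reach no lung row, and a report of zero TRALI would be largely set by the definition. Detection of lung injury by arm, and judgement of relatedness, remain in place.

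The size is modest. Expected TRALI from the study units is 0.009 to 0.018 cases. TACO is the larger omission, at 2.2 to 3.4 events per patient or 4.5 to 6.7 per unit, if the 2-3 per 100 applies to this setting. The conclusion assumes that severe injury with shock is generally regarded as a clinical risk factor for ALI. The protocol's aims and background imply this but do not state it. The change is worth making because it is cheap; it is not a must-fix.

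**What to change.** Revise the recording definitions in Table 4 and the matching case report form:

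- Keep the TRALI row as it is.
- Add a row for acute hypoxemia with bilateral infiltrates within 6 hours of study fluid or any blood component. Count it in both arms whether or not ALI risk factors are present, and record those risk factors as a descriptor.
- Add a TACO row with stated criteria, chosen by the sponsor with its transfusion medicine advisers.
- Report both new rows by arm to the DSMB.
- Apply the rows to patients already enrolled, from existing records and without knowledge of arm where possible. At least 100 had been enrolled by the second interim analysis, and counts from later patients alone would be incomplete.

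The cost is an edit to the table and form, plus chart review for earlier patients. The scheduled blood gases supply the oxygenation data. The text of IV.C.1 lists no study chest imaging, so the infiltrate criterion would rest on films from routine care.

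The downside is more events in both arms, many caused by the injury itself and some overlapping the Lung dysfunction row, so interpretation rests on the randomised comparison. Because the trial is unblinded, the criteria should be applied in the same way in each arm. Clinical management is unchanged.

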- f. Any deviation to the protocol that may have an adverse effect on the safety or rights of the subject or the integrity of the study must be reported to the HRPO and the IRB as soon as the deviation is identified.

of

- Table 5: Monitoring Schedule Equipment Product Frequency Responsible Party Exchange PCM Every 24 hours Paramedics Log of coolers of bottles Inspection of cooler box every shift Paramedics Log of coolers Plasma replaced if not 11.5 months from time of collection PRA used Plasmatherm inspection Every shift Paramedics Log checklists Clinical Lab TEG Documented -Manufacturer - every 6 months Clinical Lab in Clinical Lab - every shift Clinical Lab calibration loq -Quality control Research Lab TEG Documented
- g. A summary of the safety monitoring schedule in Table 5:

-Manufacturer calibration	- every 6 months - every week	PRAs	log
-Quality control			
Freezer for sample storage	Connected to Sensaphone alarm system at all times and physically checked once a day M-F.		
Data Monitoring			
Evaluation of data quality	Data collectors will be fully trained and observed in the first two patients to assure correct data obtention; data entry will be verified by cross checking with the medical record the data entered for the first 5 patients. Discordances between medical record (which will be considered the "gold standard") and data entry will be adjudicated by [name]. In the case there is any discordance in the primary or secondary endpoints, data collectors will be re-trained to ensure data reliability. Discordances over 5% in the variables used in the exploratory analyses will trigger re- training. At the end of the study, a random sample of 10% of the patients will have their data cross-checked with the medical records and if there are discordances with primary endpoints, all records will be reviewed to ascertain the primary endpoints. Secondary endpoints and exploratory analyses will follow the same procedure if over 5% discordance is found. Laboratory measurements defined in exploratory analyses 4, 5, and 6 follow standard procedures in the lab to ensure data integrity Daily	[name], Research Fellows, PRAs	
		Fellows, PRAs	
Verify training of newly hired paramedics	Every 4 months	Research Fellows, PRAs	
DSMB meeting	Every 6 months or sooner	DSMB	DSMB report
Interim Analysis	Per analysis plan	[name] [name]	Interim Report

